3.0 SUBJECT ELIGIBILITY

Subjects must meet all the selection criteria to be enrolled to the study. Study treatment may not begin until a subject has been consented and meets the full eligibility criteria.

3.1 Inclusion Criteria

Participants will be: (1) Age 18-55 inclusive; (2) Ability and willingness to give informed consent; (3) Confirmed diagnosis of BD based on DSM-IV criteria being met from previous enrollment in the Prechter Bipolar Longitudinal Study (HUM00000606, PI: [name]); (4) We will select BD patients scoring above published norms (upper 50th percentile) on the NEO-PI impulsivity facet ⁶ to ensure that

the recruited patients exhibit the network dysfunction targeted by the tACS paradigm and therefore have the potential to benefit from this neuromodulation technique. (5) On a stable dose of medication for 2 weeks prior to Sessions 2 & 3.

3.2 Exclusion Criteria

Participants will not have: (1) Significant neurological abnormalities, such as seizure disorder, mass lesions, etc.; (2) Known Mendelian disorder; (3) Active problematic substance use in the past 30 days (as determined by the Substance Use Disorder module of SCID); (4) Evidence of suicidal intentions or behaviors in the past month, as judged by affirmative responses to question #4 or #5 on the Columbia Suicide Severity Rating Scale (CSSRS) or report of suicidal behaviors in the last 6 months (refer to Appendix A for suicide protocol); (5) Pregnant or trying to become pregnant, or currently lactating; (6) unremovable hair extensions, braids or weaves; (7) implants or neurostimulators which could interact with applied electrical currents; (8) history of serious traumatic brain injury (loss of consciousness > 20 min)

4.0 SUBJECT SCREENING, ENROLLMENT, AND RECRUITMENT

We will recruit 30 individuals with a DSM-IV diagnosis of Bipolar Disorder (I, II, or NOS) from the Prechter Longitudinal Bipolar Disorder Study which consists of a cohort of 800+ well-characterized BD patients.⁵

4.1 Screen Failures

Those found to be ineligible to participate after the Session 1: Screening & Assessment visit will still be compensated a total of \$20 for their time. Those who leave the study early will be paid for the sessions they completed.

4.2 Blinding

Participants, study coordinator and clinical assessor will be blind as to which session the participants receive active or sham treatment. The PI and the data analyst will be aware of the intervention assignment.

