Flanker Task. After completing the Emotion Go-NoGo task, participants will perform a separate cognitive control task (i.e., Flanker task; described below). Accuracy and reaction time will be used to index cognitive control behavior as outcome measures. EEG recorded during the Flanker task will be used to assess neurological indicators of attention control. Participants will then be 50-50 randomized to receive either the Sham treatment first or tACS treatment first at Session 2.

7) Randomization. Subjects will be randomized on a 50-50 basis to receive active vs. sham stimulation. If participants are randomized to the active group at Session 2, they will go to the sham group at Session 3, and vice versa. The participant will not be told which group they were randomized to. The randomization schedule will ensure an equal distribution across the group. Randomization lists

will be generated by random condition generator and will be programmed into the computer that controls the tACS device by the postdoc fellow or PI.

Sessions 2 and 3: Sham vs. Active tACS Session (~2-3 hours)

These sessions will occur at the University of Michigan Rachel Upjohn Building. Participants will undergo two sessions, separated by ~ 1 week. Procedures will be identical for each session.

- 1) *Pre-Visit Preparations*. Research staff will contact the participant to remind them about the study visit and to ask if they have had any medication changes since their last visit. If yes, the participant will be re-scheduled for an appointment time in which the criteria for a stable dose of at least two weeks has been achieved. Additionally, participants will also be asked if they have had any recreational drug use since their last study visit. If yes, the participant will have to be re-scheduled 30 days out.
- 2) *Arrival on scheduled session day*. Participants will arrive at the Rachel Upjohn Building where they will be greeted by a member of research staff and escorted to the treatment room. Pregnancy urine test will be given if participant opted out of signing the Pregnancy Attestation Form.
- 3) *Clinician Administered Assessments*. In-person clinical assessments will be completed by a trained member of staff. All study clinicians are blinded to the treatment arm.

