- 4) *Self-Rated Assessments*. Participants will fill out BDI, ASRM, and PSWQ questionnaires. Any additional questionnaires not completed at the previous visit may be completed at this time or given to the participants to complete at home.
- 5) EEG and brain stimulation. EEG procedures will be repeated from Session 1. CF (cross frequency)-tACS targeting theta-gamma PAC will be administered in accordance to Consultant [name]'s published protocol⁴, which has successfully enhanced theta-gamma PAC and cognitive control in non-psychiatric individuals. Participants will be fitted using a montage consisting of 9 electrodes placed over the left frontal scalp.

Soterix Medical High-Definition Transcranial Alternating Current Stimulation device (HD-tACS) will be used to deliver current to the electrodes to generate tACS resembling theta-gamma PAC^{4,10,11}. The impedance of each stimulation electrode will be kept below 10 k Ω . The stimulation waveform will consist of a theta component (5 Hz) delivered at 0.96 mA (1.92 mA peak-to-peak) delivered in a constant sine wave and a gamma component (50 Hz), 3.5 cycles of a sine wave delivered at 0.64 mA (1.28 mA peak-to-peak) superimposed on the theta component and centered on the peak of each cycle. For both tACS and sham conditions, the stimulation will slowly ramp up over the course of 12 s, then the task will begin soon after maximum stimulation output is reached. Stimulation will be maintained at a stable level until the task is complete and the stimulation will ramp down over 12 s. Actual parameters may be varied slightly, but not enough to affect the risk to the participants.

tACS Study (HUM00208557)

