Previous literature suggests that participants are sensitive to stimulation until the sensory neurons in the skin acclimate to the stimulation. Thus, we will use sham stimulation as an active control condition. We will inform our participants that they will sense the stimulation in the skin but will acclimate to the stimulation soon after it begins. They will be informed that they will receive two version of the stimulation, to facilitate blinding in case the participant does not acclimate to the stimulation. For sham, a genuine cross-frequency waveform will be delivered at maximum strength for 12 s, followed by a ramp-down. The ramp-up and ramp-down during the sham stimulation is designed to mimic the feeling of acclimation that is experienced with verum stimulation due to sensory adaptation. Published data from Consultant [name]'s lab indicate that this procedure provides sufficient participant blinding to the condition⁴.

6) Cognitive Control Task (Emotion Go-NoGo Task)

Participants will engage in an Emotion Go-NoGo task to activate affective cognitive control during the baseline EEG as well as the stimulation sessions. In this task, participants view facial images exhibiting different emotions (neutral, happy, sad, or angry). For each face (150 ms), they are to press a button within 1500 ms if the face expresses the target emotion (Go trials; 80%) and withhold the response if the face expresses the distractor emotion (NoGo trials; 20%); the pairing of target and distractor emotions vary across blocks. The task includes a total of 640 trials, divided into 8 blocks of 80 trials each. Half (4) of the blocks include original face images (Easy condition), and the other half (4) include visually degraded images (Difficult condition). The two difficulty conditions are presented in alternating order (counter-balanced across participants). Accuracy (particularly on NoGo trials) and reaction time (on Go trials) will be used to index cognitive control behavior as outcome measures. [*Note: the timing and trial parameters of the actual task may be modified slightly depending on initial testing results].

- 7) *Stimulation Side Effects Questionnaire*. Participants will complete this questionnaire regarding their experience following each stimulation session. They will also be asked to rate how much the stimulation improved cognitive performance as well as if they experienced any side effects (e.g., headache, neck pain, tingling).

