7.0 STATISTICAL CONSIDERATIONS

Aim 1 - Acceptability and Tolerability. Neuromodulation studies typically use dropout rate and reported adverse events as measures of acceptability and tolerability, respectively.¹² We will compare the percentage of participants requesting to discontinue the session and the severity of side effects reported following the tACS vs. sham procedure using Bayes factors (BF).

Aim 2 - tACS Effects on Neural Synchrony and Cognitive Control Behavior. EEG data preprocessing and spectral analyses will be conducted using custom MATLAB scripts and EEGLAB following the general methods described in **PI [name]**'s published work.⁷ Briefly, data will be downsampled to 500 Hz, filtered (0.1 – 100 Hz), re-referenced to common average, segmented into short epochs (for task data, -400 to 1800 ms time-locked to onset of stimuli; for rest data, 2 s epochs), applied independent component analysis to reject non-neural artifacts, baseline adjusted, followed by automatic artifact rejection of epochs containing voltage exceeding ±100 μ V. Data will be mirrored on both ends to minimize edge artifacts, applied Morlet wavelet convolution to extract power of different frequencies from 2 to 60 Hz. Theta-gamma PAC will be computed using the Kullback-Leibler Modulation Index (KLMI)⁸ implemented in the PAC Tools plugin for EEGLAB.⁹ Neural synchrony (theta-gamma PAC) during the rest EEG blocks and cognitive control performance (sensitivity d', response bias β , and reaction time on the Emotion Go-NoGo task) will be analyzed in separate repeated-measures ANCOVAs, with stimulation (tACS, sham) as within-subjects factor.

Potential Problems & Alternative Strategies

Participants Dropout. The study design entails each participant completing all 3 sessions. Our experience of conducting multiple-session neuromodulation studies suggests that average dropout rate for each subsequent session is 10-15%. We will enroll 30 participants to ensure that at least 20 participants will complete the study even with an overall dropout of 30%.

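### The data analyst knows the assignment and nothing masks session labels during EEG cleaning, so condition-aware cleaning of rest-block theta-gamma PAC is possible, though not shown

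*Combined protocol and SAP*

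**What the plan says.** Section 4.2 (Blinding) keeps participants, the study coordinator and the clinical assessor blind to which session is active. It then says: "The PI and the data analyst will be aware of the intervention assignment". Under Randomization, Section 5.2 adds that the lists "will be programmed into the computer that controls the tACS device by the postdoc fellow or PI".

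Section 2.0 defines primary outcome 6 as theta-gamma PAC (Kullback-Leibler Modulation Index) in rest EEG blocks that lie between stimulation blocks. Section 7.0 (Aim 2) says the EEG processing "will be conducted using custom MATLAB scripts and EEGLAB following the general methods described in" the PI's published work. Among the steps it lists, the data are "applied independent component analysis to reject non-neural artifacts" and baseline adjusted, "followed by automatic artifact rejection of epochs containing voltage exceeding" ±100 µV. PAC is then compared between tACS and sham within participants.

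**The concern.** In this crossover the active and sham recordings of the same person are compared directly. If the person removing ICA components knows which session is which, and removes components differently by session, that difference goes into the estimated effect on PAC. PAC is the neural target that the trial sets out to engage. The same estimate would feed the posterior probabilities of benefit and the effect sizes that Section 7.0 (Statistical Power) offers for planning later trials. Once the files have been cleaned by someone who knows the condition, the question is hard to settle afterwards.

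**Working it through.** The plan's nearest figure is its power statement. For a two-level within-subject factor, λ = n·m·f²/(1 − r) = 20 × 2 × 0.21² / (1 − 0.8) = 8.82 on (1, 19) degrees of freedom. At α = 0.05 this gives 80.4% power, against the 80% stated. The figure reproduces, but it concerns precision and says nothing about bias from cleaning. The point rests on the text, taken in five steps.

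**1. Who is masked.** The other blinding text covers the design label (Section 2.0), participants and study clinicians (Section 5.2), and unblinding for adverse events (Section 6.6). None of it covers EEG processing. The available text contains no coded session labels and no lock of cleaned data before labels are attached.

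**2. Which cleaning steps are fixed.**

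| Step in Section 7.0 | What is fixed | What is left open |
|---|---|---|
| Resampling, filtering, re-referencing | 500 Hz; 0.1–100 Hz; common average | – |
| Epoching | "for task data, -400 to 1800 ms time-locked to onset of stimuli; for rest data, 2 s epochs" | – |
| ICA | Its purpose only | Component rule; who applies it; whether rest and task data are decomposed together |
| Epoch rejection | Automatic, ±100 µV | – |
| PAC | Index and software plugin named | – |

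ICA component rejection is the cleaning step where the text gives neither a rule nor an operator.

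**3. How a difference would reach the estimate.** As a simple additive model, let cleaning shift a person's PAC by c(tACS) in one session and c(sham) in the other. The estimated contrast then has expectation

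true effect + [c(tACS) − c(sham)].

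Cleaning that acts equally on both sessions cancels. Cleaning that follows the condition does not cancel. Randomised order does not help, because order balances effects of period, and this shift would be tied to condition.

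**4. Which outcomes are exposed.** Side-effect severity and withdrawal do not use EEG. Sensitivity, response bias and reaction time come from button presses and are a weaker route. That leaves mainly one of the six primary outcomes.

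**5. Whether relabelling alone would mask the files.** It would not for whole-session recordings. In the active session, "Stimulation will be maintained at a stable level until the task is complete"; in the sham session, "a genuine cross-frequency waveform will be delivered at maximum strength for 12 s, followed by a ramp-down". The stimulation trace would reveal the condition, so masking has to be applied to rest-block segments. Whether segments without stimulation can be cut is unclear. Section 2.0 places rest blocks between stimulation blocks, while Section 5.2 describes current held until the task ends. These two passages must be reconciled on whether current is off during the rest blocks.

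**The case against.** The strongest reply is that this is an openly stated design choice. Section 4.2 says who is blind and who is not, and the people who supply or rate participant-facing data are covered. That stands: there is no contradiction and nothing is hidden.

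A second reply is that Section 7.0 calls its account brief and defers to published general methods, which may contain a component rule or an automated procedure. The documents also do not say that the analyst does the cleaning; a blinded person might. Both points stand, and they limit the weight of the concern. They do not remove it, because a component rule would not in itself mask session labels, and nothing requires a blinded person to do the cleaning.

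A third reply is that this is a small study meant to give preliminary estimates. That supports a low priority. It also means the estimates themselves are the product, since later trials are to be sized from them.

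A reader might infer more: that component rejection is discretionary and done with knowledge of the condition, so that the PAC result will be biased. The documents do not support this. They name no operator, describe no manual selection, and show only that nothing prevents it.

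**Conclusion.** The point holds as a gap in protection. The analyst's awareness is an explicit rule, no available text masks EEG processing, and one cleaning step before primary outcome 6 has no stated rule or operator. It rests on two assumptions: that the cited methods do not already impose masking, and that text not available for review does not do so either.

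No size can be given. A reader might be tempted to posit a shift in PAC and calculate an inflated type I error, but no document supplies such a shift. The answer would describe a generic paired comparison and not this trial. Nor does the analyst's awareness make the double-blind label false for participants and assessors, whose blinding Section 4.2 keeps.

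This is a low-priority, cheap improvement, mainly for one of six primary outcomes.

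**What to change.** Change Section 4.2, with a matching sentence in Section 7.0:

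1. Whoever carries out ICA component rejection and PAC derivation works on rest-block files of Sessions 2 and 3 that carry neutral session codes.
2. The key is held by someone already aware of the assignment who does not clean data, for example the PI or the postdoc fellow who loads the randomisation list. It is not held by the coordinator or clinical assessor, who must stay blind.
3. The component-rejection rule is fixed in advance and applied identically to both sessions.
4. Component rejections, epoch rejections and PAC values are locked before the key is released.
5. Sections 2.0 and 5.2 are reconciled on whether current is off during rest blocks. If stimulation-free segments cannot be cut, or if rest and task data must be decomposed together, rely on the pre-specified or automated component rule and report the number of components rejected by condition.

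The cost is a relabelling and lock step for two sessions per participant, and possibly poorer ICA if rest data are decomposed alone. Residual stimulation artifact in the rest segments could still reveal the condition, so masking reduces the risk but may not remove it.

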4.3 Subject Recruitment and Retention

We will recruit 30 individuals with a DSM-IV diagnosis of Bipolar Disorder (I, II, or NOS) from the Prechter Longitudinal Bipolar Disorder Study which consists of a cohort of 800+ well-characterized BD patients.⁵ Participants are expected to match the sex and racial composition of the Longitudinal study (50% female, 50% male; 81% white, 12% African-American, 6% Asian, 1% Other). Participants who are enrolled in the Prechter Study, and who have been identified by the Prechter Study staff as possible participants, will be emailed a description of this study, including contact information about how to learn more.

Pre-screening will occur when the study coordinator contacts the potential participant, via phone or email to discuss a series of eligibility questions. Patients who appear eligible in the pre-screen will be invited for an initial assessment session. Reminder calls, emails and/or texts will be provided to subjects before each scheduled session.

5.0 STUDY ASSESSMENTS AND PROCEDURES

5.1 Assessments

Clinician Administered Assessments (~ 60 mins):

- 1) Demographic/medical history form
- 2) Structured Clinical Interview for DSM-IV (SCID-IV), substance use disorder only (Module E). Note: Subjects endorsing unhealthy substance use in the last 30 days but do not meet full criteria for abuse or dependence will be given a urine drug screen.
- 3) The Mental Illness Research, Education and Clinical Centers Global Assessment Functioning (MIRECC GAF)
- 4) Social and Occupational subscales only Young Mania Rating Scale (YMRS) scale to grade the severity of mania symptoms
- 5) Hamilton Depression Rating Scale (HAM-D) scale to grade severity of depression
- 6) Columbia-Suicide Severity Rating Scale (C-SSRS)

Self-Rated Assessments (~ 30 mins):

- 1) Beck Depression Inventory (BDI)
- 2) Altman Self-Rating Mania Scale (ASRM)
- 3) Barratt Impulsiveness Scale (BIS)
- 4) Behavioral Inhibition System/Behavioral Activation System (BIS/BAS)
- 5) Stimulation Side Effects Questionnaire
- 6) Penn State Worry Questionnaire (PSWQ)

5.2 Procedures

The following procedures will be conducted in-person following the University of Michigan's Covid safety protocols.

Pre-Visit Preparations. Participants who meet criteria after initial phone screening, will be scheduled for three in-person sessions at the Rachel Upjohn Building. Participants will be emailed a blank copy of the consent form to review prior to their visit.

Session 1: Screening & Assessment (~ 2-3 hours)

Informed Consent. Formal consent will be obtained at the beginning of the visit. The participant will arrive at the Rachel Upjohn Building at the University of Michigan East Ann Arbor Health Campus. A study coordinator or a trained research assistant will greet the participant and take them to a private interview room where the study will be explained, the consent form reviewed, and any questions answered. Participants will have the option to electronically consent (using SignNow, according to IRBMED guidelines) prior to the in person visit through a Zoom meeting with one of the study team members.

Pregnancy Screening. All woman of childbearing age will be asked during their screening whether they are pregnant or are trying to become pregnant and will not be enrolled in the study if they are. They will be given an option for a urine pregnancy test at the start of each session. Woman with a positive pregnancy test will not be permitted in the study. They may decline this option and sign a pregnancy attestation form at each session indicating that they do not believe they could be pregnant.

Sexually active women of childbearing potential will be required to use a reliable birth control method for the duration of this study.

- 2) *Clinician Administered Assessments*. This interview process will be conducted to determine a participant's inclusion/exclusion eligibility. If the participant is ineligible to participate in the study, the rationale for their exclusion will be explained to them.
- 3) Urine Drug Screening (UDS). Participants who screened positive for current substance use disorder will be administered a UDS. If their UDS indicates the presence of a substance, they will not undergo that day's visit. At the PI's discretion, the participant may be given the option to abstain from all substance use and be rescheduled to provide another urine sample. If they have a clean UDS at that time, they will be able to continue with the visit at that time. Those that are not given the option or who refuse to do the UDS will be a screen fail. Participants who have no active current substance use will not be required to provide a urine sample.
- 4) *Self-Rated Assessments*. Participants deemed eligible will complete self-rated assessments and computerized tasks through Qualtrics, using an anonymous survey link. No identifiable information will be collected within the survey.
- 5) *Baseline EEG*. EEG will be recorded using a 64-channel electrode cap using EEG procedures that are standard in cognitive ERP and time-frequency analysis research. The cap is an elastic cap that fits snugly over the scalp of the participant, holding the electrodes in place. A standard conductive electrode gel will be inserted into each electrode using a blunt-needle syringe. The scalp will be gently rubbed with a swab to improve electrode impedance (i.e., to lower the electrical resistance). Typical application time for an electrode cap lasts around 30 minutes. The electrode for monitoring eye movements will be affixed with adhesive collars. The skin will also be cleaned with an alcohol swab for this electrode. The cap and electrodes will be disinfected after each use with a disinfectant recommended by BrainVision Company (e.g., Cavicide). Other items will be disposed of after each use. The experimenter will wipe the residual electrode gel from the participant's hair and skin after the EEG session.

Emotion Go-NoGo Task. Participants will undergo an EEG and perform a cognitive control task (Emotion Go-NoGo task; described below).

Flanker Task. After completing the Emotion Go-NoGo task, participants will perform a separate cognitive control task (i.e., Flanker task; described below). Accuracy and reaction time will be used to index cognitive control behavior as outcome measures. EEG recorded during the Flanker task will be used to assess neurological indicators of attention control. Participants will then be 50-50 randomized to receive either the Sham treatment first or tACS treatment first at Session 2.

7) Randomization. Subjects will be randomized on a 50-50 basis to receive active vs. sham stimulation. If participants are randomized to the active group at Session 2, they will go to the sham group at Session 3, and vice versa. The participant will not be told which group they were randomized to. The randomization schedule will ensure an equal distribution across the group. Randomization lists

will be generated by random condition generator and will be programmed into the computer that controls the tACS device by the postdoc fellow or PI.

Sessions 2 and 3: Sham vs. Active tACS Session (~2-3 hours)

These sessions will occur at the University of Michigan Rachel Upjohn Building. Participants will undergo two sessions, separated by ~ 1 week. Procedures will be identical for each session.

- 1) *Pre-Visit Preparations*. Research staff will contact the participant to remind them about the study visit and to ask if they have had any medication changes since their last visit. If yes, the participant will be re-scheduled for an appointment time in which the criteria for a stable dose of at least two weeks has been achieved. Additionally, participants will also be asked if they have had any recreational drug use since their last study visit. If yes, the participant will have to be re-scheduled 30 days out.
- 2) *Arrival on scheduled session day*. Participants will arrive at the Rachel Upjohn Building where they will be greeted by a member of research staff and escorted to the treatment room. Pregnancy urine test will be given if participant opted out of signing the Pregnancy Attestation Form.
- 3) *Clinician Administered Assessments*. In-person clinical assessments will be completed by a trained member of staff. All study clinicians are blinded to the treatment arm.
- 4) *Self-Rated Assessments*. Participants will fill out BDI, ASRM, and PSWQ questionnaires. Any additional questionnaires not completed at the previous visit may be completed at this time or given to the participants to complete at home.
- 5) EEG and brain stimulation. EEG procedures will be repeated from Session 1. CF (cross frequency)-tACS targeting theta-gamma PAC will be administered in accordance to Consultant [name]'s published protocol⁴, which has successfully enhanced theta-gamma PAC and cognitive control in non-psychiatric individuals. Participants will be fitted using a montage consisting of 9 electrodes placed over the left frontal scalp.

Soterix Medical High-Definition Transcranial Alternating Current Stimulation device (HD-tACS) will be used to deliver current to the electrodes to generate tACS resembling theta-gamma PAC^{4,10,11}. The impedance of each stimulation electrode will be kept below 10 k Ω . The stimulation waveform will consist of a theta component (5 Hz) delivered at 0.96 mA (1.92 mA peak-to-peak) delivered in a constant sine wave and a gamma component (50 Hz), 3.5 cycles of a sine wave delivered at 0.64 mA (1.28 mA peak-to-peak) superimposed on the theta component and centered on the peak of each cycle. For both tACS and sham conditions, the stimulation will slowly ramp up over the course of 12 s, then the task will begin soon after maximum stimulation output is reached. Stimulation will be maintained at a stable level until the task is complete and the stimulation will ramp down over 12 s. Actual parameters may be varied slightly, but not enough to affect the risk to the participants.

tACS Study (HUM00208557)

Previous literature suggests that participants are sensitive to stimulation until the sensory neurons in the skin acclimate to the stimulation. Thus, we will use sham stimulation as an active control condition. We will inform our participants that they will sense the stimulation in the skin but will acclimate to the stimulation soon after it begins. They will be informed that they will receive two version of the stimulation, to facilitate blinding in case the participant does not acclimate to the stimulation. For sham, a genuine cross-frequency waveform will be delivered at maximum strength for 12 s, followed by a ramp-down. The ramp-up and ramp-down during the sham stimulation is designed to mimic the feeling of acclimation that is experienced with verum stimulation due to sensory adaptation. Published data from Consultant [name]'s lab indicate that this procedure provides sufficient participant blinding to the condition⁴.

6) Cognitive Control Task (Emotion Go-NoGo Task)

Participants will engage in an Emotion Go-NoGo task to activate affective cognitive control during the baseline EEG as well as the stimulation sessions. In this task, participants view facial images exhibiting different emotions (neutral, happy, sad, or angry). For each face (150 ms), they are to press a button within 1500 ms if the face expresses the target emotion (Go trials; 80%) and withhold the response if the face expresses the distractor emotion (NoGo trials; 20%); the pairing of target and distractor emotions vary across blocks. The task includes a total of 640 trials, divided into 8 blocks of 80 trials each. Half (4) of the blocks include original face images (Easy condition), and the other half (4) include visually degraded images (Difficult condition). The two difficulty conditions are presented in alternating order (counter-balanced across participants). Accuracy (particularly on NoGo trials) and reaction time (on Go trials) will be used to index cognitive control behavior as outcome measures. [*Note: the timing and trial parameters of the actual task may be modified slightly depending on initial testing results].

- 7) *Stimulation Side Effects Questionnaire*. Participants will complete this questionnaire regarding their experience following each stimulation session. They will also be asked to rate how much the stimulation improved cognitive performance as well as if they experienced any side effects (e.g., headache, neck pain, tingling).
- 8) Flanker Task. After completing the Emotion Go-NoGo task, brain stimulation, and Stimulation Side Effect Questionnaire, participants will perform a separate cognitive control task (i.e., Emotional Flanker task). Participants will complete the Emotional Flanker task to evaluate the impact of brain stimulation on cognitive control after stimulation has been completed (i.e., offline effects). Participants will perform a modified Eriksen flanker task in which gray-scaled unpleasant (e.g., injured limbs, barking dog), pleasant (e.g., cute animals, erotic pictures), and neutral stimuli (e.g., lamp, spoon) images from the International Affective Picture System (IAPS) will appear on a computer display. There will be two parts to this task: (1) Unpleasant vs Neutral and (2) Pleasant vs Neutral. Three images will be presented with congruent (e.g., unpleasant unpleasant unpleasant) and incongruent (e.g., unpleasant -neutral- unpleasant) conditions. Participants will be instructed to respond by pressing one of two buttons indicating the valence of the central image (i.e., unpleasant versus neutral), while ignoring the adjacent images, and to respond as quickly and accurately as possible. The stimuli will remain on the screen for ~400 ms in the initial block, with an interval of about ~4000 ms between consecutive stimuli. Following a practice block of 30 trials, each participant will complete 10 blocks of 30 trials for a total of 300 trials for each part (Unpleasant vs Neutral and

Pleasant vs Neutral), and a grand total of 600 trials. Performance feedback will be provided and the stimuli presentation time will be adjusted based on performance after each block (e.g., if performance is above 90%, a 40ms shorter presentation time will be used in the next block) to ensure adequate number of errors and consistency in performance across participants within each part. Actual presentation and interval time may differ slightly in implementation from that described above. Estimated to take ~40 minutes. This task is designed to assess error and response monitoring within emotional contexts, which has been shown to be different from monitoring in other contexts, such as emotionally neutral context using arrows. Accuracy and reaction time will be used to index cognitive control behavior as outcome measures. EEG recorded during the Emotional Flanker task will be used to assess neurological indicators of attention control. [*Note: the timing and trial parameters of the actual task may be modified slightly depending on initial testing results. In order to reduce subject burden, experimenters may shorten the task and drop the display of pictures (neutral and valenced), using simple arrow cues instead to indicate a right or left button press].

Follow-up Phone Call (~ 5-10 min)

Approximately 4 weeks (+/- \sim 7 days) following the completion of Session 3, research staff will call to administer the Stimulation Side Effect Questionnaire as a final safety check and evaluate for any other possible side effects.

Stopping Rules

If a participant reports intolerable discomfort during the tACS procedure, the session will be discontinued. Immediately after each stimulation session ends, participants will complete a tACS side effects questionnaire. A study team member will review the responses and will immediately consult the PI if a participant reports a high (3) to very high (4) rating for any of the side effects rated to be related to the stimulation (4=probable or 5=definite). Subjects may also be withdrawn by the investigator when continued participation would present an unacceptable risk (e.g., worsening symptoms, suicidal thoughts, etc.).

